2.1.4.2 Ocular examination

Specific ocular evaluations are planned at baseline and will be repeated at the time of the occurrence in ocular toxicity. Moreover tonometry will be performed at screening, end of cycle 6 and end of treatment.

2.1.4.3 Deaths

The deaths observation periods are per the observation periods defined above.

- Death on-treatment: deaths occurring during the TEAE period.
- Death post-treatment: deaths occurring during the post-treatment period.

2.1.4.4 Laboratory safety variables

Laboratory data consists of blood analysis, including hematology and biochemistry.

Blood samples for clinical laboratories will be taken at Day 8, Day 15 and Day 21 during the first two cycles (except for INR only at Day 21) and then at Day 8 and Day 21 for hematology and Day 21 for clinical chemistry and INR at subsequent cycles and then at end of treatment. The laboratory parameters will be classified as follows:

- Hematology:
 - **Red blood cells (RBC) and platelets and coagulation:** hemoglobin, platelet count, international normalized ratio (INR).
 - **White blood cells (WBC):** WBC with differential (neutrophils, lymphocytes, monocytes, basophils, eosinophils), absolute neutrophil count (ANC).

- Clinical chemistry:
 - **Metabolism:** blood glucose, lactate Dehydrogenase (LDH), total protein, albumin,
 - **Electrolytes:** sodium, potassium, chloride, calcium, corrected serum calcium (calculated according to Corrected calcium formula, see [Section 2.5.1](#)), phosphate,
 - **Renal function:** serum creatinine, creatinine clearance (calculated according to both Cockcroft-Gault formula, see [Section 2.5.1](#)), urea or blood urea nitrogen (BUN),
 - **Liver function:** alanine aminotransferase (ALT), aspartate aminotransferase (AST), alkaline phosphatase, total and direct bilirubin.

Moreover, serum pregnancy test will be performed at baseline, during on-treatment period and end of treatment period for women of child bearing potential.

Laboratory values will be analyzed after conversion into standard international units by data management. These converted values will be graded according to the NCI-CTCAE version 4.03 whenever applicable, using laboratory normal ranges (liver function tests, creatinine, creatinine clearance, LDH) provided by the laboratory analyzing the sample whenever possible or using generic normal ranges for other parameters (see Appendix G). When the NCI-CTCAE is not applicable, laboratory values “out of normal ranges” will be summarized.

For each laboratory parameter, each assessment performed from the 2nd day of cycle N to the 1st day of cycle N+1 will be assigned to cycle N. The 1st day of any cycle will be the date of the 1st study treatment infusion for this cycle.

Parameters measured on the day of the first study treatment infusion (Cycle 1 Day 1) will be considered as baseline measurements. If missing, the baseline measurement will be the last available value before first study treatment infusion. For a given parameter, a patient will be considered as evaluable if at least one measure of this parameter is available during the on-treatment period.

Technical formulas are described in [Section 2.5.1](#).

2.1.4.5 Vital signs variables

Vital signs include blood pressure (systolic and diastolic), BSA and body weight. Moreover ECOG performance status will be also provided. All of these parameters will be performed at screening, Days 8, 15 and 21 in Cycles 1 and 2 and Days 8 and 21 in subsequent cycles and then at end of treatment visit. ECOG PS and body weight will be also assessed in follow-up.

Parameters measured on the day of the first study treatment infusion (Cycle 1 Day 1) will be considered as baseline measurements. If missing, the baseline measurement will be the last available value before first study treatment infusion. For a given parameter, a patient will be considered as evaluable if at least one measure of this parameter is available during the on-treatment period.

2.1.4.6 Electrocardiogram variables

ECGs will be recorded automatically by the device at the Investigator site at screening and end of treatment visit.

Electrocardiogram assessments will be described as normal or abnormal.

For ECG, parameters measured during the screening period will be considered as baseline measurements.

2.1.5 Pharmacokinetic variables

Pharmacokinetic samples of SAR566658, unconjugated maytansinoids (DM4 and Me-DM4) and naked hu-DS6 will be collected at specific time points of each cycle, and at the end of treatment and follow-up visits as specified in the PK/immunogenicity flow chart of the protocol.

Main PK parameters that will be provided should include C_{max} , AUC, total clearance, distribution volume, and half-life.

2.1.6 Immunogenicity endpoints

Blood samples must be taken on Day 1 before the first study treatment infusion of each treatment cycle, then at the end of study treatment (Day 30) and at follow up (Day 60). For each time point, results are defined as negative, positive or inconclusive according to circulating levels of SAR566658.

Periods of observation:

- **Antitherapeutic antibodies (ATA) pre-treatment period:** The ATA pre-treatment period is defined as the time from signed informed consent to the first SAR566658 infusion administration.
- **ATA on-study observation period:** the ATA on-study observation period is defined as the time from first SAR566658 infusion administration until the end of the study.

ATA attributes:

- **Pre-existing ATAs** are defined as ATAs that were present in samples drawn during the pretreatment period.
- **Treatment boosted ATAs** are defined as pre-existing ATAs with an increase in titer value between pre-treatment and post-treatment samples of at least two titer steps. Assuming a 2-fold serial dilution schema is used for the study, this means that the post-treatment sample titer value is at least (\geq) 4 fold of pretreatment titer value.
- **Treatment induced ATAs** are defined as ATAs that developed at any time during the ATA on-study observation period in patients without pre-existing ATAs, including

patients without pretreatment samples. If baseline sample is missing, baseline is considered by default as ATA negative, and thus, ATA is considered as treatment-induced.

- **Transient ATA response** is defined by:
 - Treatment-induced ATA detected only at one sampling time point during the ATA on-study observation period (excluding the last sampling time point), OR
 - Treatment-induced ATA detected at two or more sampling time points during the treatment (including follow-up period if any), where the first and last ATA -positive samples (irrespective of any negative samples in between) are separated by a period less than 16 weeks and the subject's last sampling time point is ATA -negative.
- Persistent ATA response is defined by:
 - Treatment-induced ATA detected at two or more sampling time points during the ATA on-study observation period, where the first and last ATA -positive on-study samples are separated by a period of 16 weeks or longer (irrespective of any negative samples in between), OR
 - Treatment-induced ATA detected in the last two sampling time points (both positive), irrespective of the time period in between.
- **Indeterminate ATA** is defined by treatment induced ATA that is not persistent or transient (only the last sampling time is positive).

Among evaluable population for immunogenicity (see [Section 2.3.5](#) for definition), following patients will be defined:

- **ATA positive patients**, which are defined as patients with at least one treatment-induced or treatment-boosted ATA positive sample at any time during the on-study observation period;
- **ATA negative patients**, which are defined as patients without treatment-induced nor treatment-boosted ATA positive sample during the on-study observation period;
- **ATA inconclusive patients**, which are defined as patients which cannot irrefutably be classified as ATA negative.

Two main categories can be reported for the epidemiology of an ATA immune response: ATA prevalence and ATA incidence:

- ATA prevalence defines the proportion of all patients tested positive for ATAs (including preexisting antibodies, treatment boosted ATA and treatment induced ATA) at any point in time.
- In contrast, the term ATA incidence only defines the proportion of patients found to either have seroconverted (treatment induced ATAs) or boosted their pre-existing ATA response during the study.

The incidence will be defined as follows:

$$ATA\text{ incidence} = 100 \times \frac{\text{treatment boosted} + \text{treatment induced ATA positive patients}}{\text{number of evaluable patients}}$$

$$\text{Treatment induced ATA incidence} = 100 \times \frac{\text{treatment induced ATA positive patients}}{\text{number of evaluable patients ATA negative at baseline}}$$

$$\text{Treatment boosted ATA incidence} = 100 \times \frac{\text{treatment boosted ATA positive patients}}{\text{number of evaluable patients ATA positive at baseline}}$$

2.1.7 Biomarkers

2.1.7.1 Main biomarkers

CA6 expression level in tumor tissue samples by IHC

IHC will be the reference assay to assess CA6 expression level and will be performed at a central laboratory. At prescreening, determination of CA6 positivity in tumors will be performed by IHC on FFPE slides collected from the most recent available tumor samples. A total of 6 4-micron sections cut from the most recent available FFPE tumor block (ie, archive tumor tissue at diagnosis, archive tumor tissue at surgery, or most recent tumor sample) will be collected and sent to a centralized laboratory for CA6 staining by muDS6-IHC and for appropriate control. Staining will be analyzed by a dedicated pathologist. Stained and unstained slides will be kept for up to 5 years from the completion of the clinical study.

Both the membrane and cytoplasmic staining will be recorded for the percent of tumor cells positive at all intensities (1+, 2+, and 3+).

The following variables will be derived based on the percentage of positive cells at all intensities (1+, 2+, and 3+):

- Percentage of positive cells at intensity $\geq 2+$ on the sum of membrane, quantitatively and by categories.
- H-score on the sum of membrane (either whole or polarized) staining. H-score will be defined by $([\% \text{ positive cells at intensity } 0] \times 0 + [\% \text{ positive cells at intensity } 1+] \times 1 + [\% \text{ positive cells at intensity } 2+] \times 2 + [\% \text{ positive cells at intensity } 3+] \times 3)$.
- Main analyses will be performed on membrane staining but descriptive analyses on cytoplasmic staining could eventually be explored.

Circulating CA6 from blood samples

A blood sample will be collected at baseline prior to the first treatment administration and plasma will be extracted on site. Plasma will be stored at -70°C or below and transferred on a planned schedule to a centralized laboratory until their authorized transfer to a testing laboratory, where circulating CA6 levels will be determined. Circulating CA6 will be determined by a semiquantitative sandwich enzyme-linked immunosorbent assay (ELISA).

2.1.7.2 Exploratory pharmacodynamic biomarker

[REDACTED]

[REDACTED]

[REDACTED]

2.1.7.3 Other exploratory biomarkers

[REDACTED]

[REDACTED]

[REDACTED]

[REDACTED]

2.1.8 Post-treatment therapy after discontinuation of investigational medicinal product administration during the study

Post treatment anti-cancer therapies include post treatment systemic anti-cancer treatment (including chemotherapy, hormonal therapy, immunotherapy...), post treatment radiotherapy (other than given in palliative intent) and post treatment surgery related to cancer.

[figure not shown]
Palliative radiotherapy may be given for control of pain for palliative intents during treatment period. This will not be considered as post treatment anti-cancer therapy and thus will be documented separately.

2.2 DISPOSITION OF PATIENTS

This section describes patient disposition for both patient study status and the patient analysis populations.

An overview of the analysis populations is presented in the [Figure 1](#).

Figure 1 : Analysis population

Pre-registered (pre-screened) patients are defined as patients who signed the prescreening informed consent for CA6 assay assessment of their archival biopsy

Registered (screened) patients are defined as patients who signed the informed consent for study participation and are planned to enter in the screening period, i.e. for whom the investigator ticked “Yes” to the question “Will the subject continue in the screening phase of part 1 (or part 2)?” at the end of prescreening period.

Enrolled patients includes registered patients who are planned to enter in the study period, ie, for whom the investigator ticked “Yes” to the question “Will the subject continue in the Treatment

phase?” at the end of screening period. In part 1, patients also need a confirmation of a successful allocation of a randomization number through the IVRS/TWRS in order to be randomized.

The total number of patients in each of the following analyses population will be presented in the clinical study report using a flowchart diagram or a summary table:

- Pre-registered population
- Registered population
- Not enrolled but treated population
- Enrolled population
- Enrolled but not treated population
- All-treated population
- Evaluable for predefined safety criteria population
- Response evaluable population

For patient study status, the total number of patients in each of the following categories will be presented in the clinical study report using a flowchart diagram or a summary table:

- Enrolled patients
- Enrolled and not treated patients with reason for non-treatment
- All-treated population with number of patients who discontinued study treatment by main reason for treatment discontinuation
- Status at last study contact: alive, dead

For all categories of patients (except for the pre-registered, registered and not enrolled patients) percentages will be calculated using the number of enrolled patients as the denominator.

All critical or major deviations will be summarized in tables giving numbers and percentages of deviations.

2.2.1 Randomization irregularities

Randomization irregularities occur whenever a randomization is not in accordance with the protocol-defined randomization method, such as a) an ineligible patient is randomized, b) a patient is randomized based on an incorrect stratum, c) a patient is randomized twice.

All randomization irregularities will be documented in the clinical study report. If the number of irregularities is large enough to make a tabular summary useful, the irregularities will be categorized and summarized among the treated patients (number and percentages). Nonrandomized/non enrolled but treated patients will be described separately. Listings with additional, relevant details will be provided in an appendix, eg, excluded second randomization/enrollment study data for patient randomized/enrolled twice.

Randomization irregularities to be prospectively identified include but are not limited to:

Randomization irregularities
Randomization by error
Patient randomized twice
Stratification error
CA6 level expression error
Patient switched to another site

2.2.2 Important deviations potentially impacting efficacy

The summary of important protocol deviations will be based on the all treated population. Other deviations will not be summarized in the Clinical Study Report.

Important protocol deviations are based on inclusion/exclusion criteria and are defined as follows:

- No metastatic TNBC (I01),
- Patient with no measurable disease as per RECIST 1.1 (I02),
- No histologically documented TNBC (I03),
- Not the corresponding CA6 membrane expression level according the threshold defined in the study part (I04),
- No prior chemotherapy regimen or more or equal to 4 for advanced/metastatic disease (I05),
- No prior anticancer therapy with anthracycline and a taxane in an adjuvant/neoadjuvant or metastatic setting (I06),
- Prior treatment with eribulin as last prior therapy or prior maytansinoid treatments (E13).

2.3 ANALYSIS POPULATIONS

Patients treated without being randomized (missing the third call IVRS in the Part 1) will not be considered randomized and will not be included in any efficacy or all treated population.

For any patient randomized or enrolled more than once, only the data associated with the first randomization will be used in any analysis population. The safety experience associated with any later randomization will be assessed separately.

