11.3.1 Safety population

The all treated population consisting of patients who will actually receive at least 1 dose (or any partial) of SAR566658. This population is the primary population for the analyses of efficacy and safety parameters.

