2.3.1.1 All treated population

The all-treated population (AT) consists of enrolled patients who will actually receive at least one dose or any partial of a dose of study treatment.

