2.3.2 Safety population

The population used for safety analyses consists of the all-treated population. Any safety analysis will be performed on this population

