2.4 STATISTICAL METHODS

Continuous data will be summarized using the number of available data, mean, standard deviation, median, minimum, Q1, Q3 and maximum. Categorical and ordinal data will be summarized using the number and percentage of patients.

All the tables will be presented by the intended dose level in the Part 1 and by actual expression cohort at the selected dose in the Part 2 (mild expression or overexpression cohorts). Separate tables will be provided for Part 1 and Part 2. Summary table including both dose levels and expression cohorts will be provided for some analyses as demographics or analysis population topics.

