2.4.5.2 Deaths

The following summaries of deaths will be generated for the all-treated population:

- Number (%) of patients who died by study period (on-treatment, post-treatment as defined in [Section 2.1.4.3](#)) and reasons for death by treatment received.
- Deaths in nonrandomized patients or randomized but not treated patients. A listing may be provided.

- Summary of AEs leading to death, by Primary SOC and PT
 - in context of disease progression (death within 30 days from last study treatment administration and for whom cause of death is disease progression),
 - in context other than PD (death within 30 days from last study treatment administration and for whom cause of death is different from disease progression, or death more than 30 days from last study treatment administration and for whom cause of death equals to adverse event)

Some listings might also be reported if judged more relevant.

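### The SAP narrows the protocol's safety population and tabulates Part 1 by intended dose, so summarised toxicity need not follow the drug actually given

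*SAP*

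**What the plan says.** **Population.** Protocol 11.3.1 makes the safety population the "patients who will actually receive at least 1 dose (or any partial) of SAR566658". Enrollment and randomization are not conditions, and the same set is primary for efficacy. Protocol 11.4.5 places all safety analyses on it.

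The SAP adds conditions. Section 2.3.1.1 reads "The all-treated population (AT) consists of enrolled patients who will actually receive at least one dose". Section 2.3 says that Part 1 patients dosed without the third IVRS call "will not be included in any efficacy or all treated population". Section 2.3.2 then states: "The population used for safety analyses consists of the all-treated population". SAP 1.6, which is the place for statistical modifications made in the SAP, is marked not applicable.

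The excluded patients are still reported. SAP 2.4.5 lists their safety data separately, SAP 2.2.1 has them described separately, and SAP 2.2 counts treated patients who were not enrolled as a category of their own.

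**Dose grouping.** SAP 2.4 says: "All the tables will be presented by the intended dose level in the Part 1". The safety section (SAP 2.4.5) refers only to dose levels and does not say whether intended or received. SAP 2.4.5.2 presents "reasons for death by treatment received".

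**PSC and Bayesian monitoring.** SAP 2.3.3 defines a separate evaluable population in terms of patients treated, and SAP 1.1 triggers the model once 4 patients treated at 120 mg/m² are evaluable. SAP 2.3.2, however, extends its population to any safety analysis.

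**The concern.** Part 1 exists to choose between two doses on response and safety, with 14 patients per dose, and PSC incidence in Cycles 1 and 2 is its primary safety endpoint. Grouping by allocation is defensible for efficacy. Toxicity is caused by exposure, so it should be counted in everyone exposed and under the dose they received.

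The SAP as written departs from that in two ways. A dosed but unrandomized patient contributes to neither the numerator nor the denominator of any all-treated safety table. A patient allocated to one dose but given the other has her adverse events tabulated under the dose she did not receive, and her death, if it occurs, under the dose she did. Two tables in one report would then place the same patient in different arms. In arms of this size a single patient visibly changes the comparison on which the dose decision rests.

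**Working it through.** **1. The plan's own safety figures.** SAP Appendix A gives the posterior at 120 mg/m² as Beta(0.5 + 2k' + x, 0.5 + 8k' − 2k' + n − x), with k' = 0.2.

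- First prior parameter: 0.5 + 0.4 = 0.9.
- Second prior parameter: 0.5 + 1.6 − 0.4 = 1.7.
- Posterior: Beta(0.9 + x, 1.7 + n − x).
- GO requires P(rate > 0.40) ≤ 25% and P(rate > 0.60) ≤ 5%.

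The recomputed values match the SAP:

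| PSC / n | P(>0.40) | P(>0.60) | Decision | SAP source |
|---|---|---|---|---|
| 1/4 | 24.20% | 4.64% | GO | Table 13 |
| 2/4 | 56.58% | 20.25% | No GO | Table 13 |
| 2/8 | 17.26% | 1.38% | GO | Table 15 |
| 3/8 | 39.52% | 6.15% | No GO | Table 15 |

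The posterior probabilities and decisions in Tables 8 to 15 all reproduce. The arithmetic of the model is not in question.

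**2. Effect on the tabulated rates.** The documents give no expected number of affected patients, so these are illustrations that assume exactly one. With none, nothing changes.

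- *One wrongly dosed patient.* Assume 3/14 (21.4%) with a PSC in each arm as intended, and that one of the three at 90 mg/m² actually received 120 mg/m². By dose received, 120 mg/m² has (3 + 1)/(14 + 1) = 4/15 = 26.7% and 90 mg/m² has (3 − 1)/(14 − 1) = 2/13 = 15.4%. The gap is 11.3 points, against 0 in the intended-dose table.
- *Upper end for one such patient.* With 0/14 at 120 mg/m² and 1/14 at 90 mg/m² as intended, the rates by dose received are 1/15 and 0/13. The between-arm difference shifts by 1/15 + 1/14 = 6.7 + 7.1 = 13.8 points.
- *One unrandomized dosed patient with a PSC.* She is additional to the 14, so 3/14 = 21.4% becomes 4/15 = 26.7%, a change of 5.2 points.

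**3. What would follow if the exclusion also governed the Bayesian model.** Leaving out a patient removes her from x and from n, so both must change:

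| Left out | Counted | Result |
|---|---|---|
| 1/4: 24.20% / 4.64%, GO | 2/5: 43.63% / 10.89%, No GO | Recommendation changes |
| 2/7: 23.98% / 2.82%, GO | 3/8: 39.52% / 6.15%, No GO | Recommendation changes |
| 0/4: 4.56% / 0.44%, GO | 1/5: 16.34% / 2.12%, GO | No change |

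Whether the exclusion does govern the model cannot be settled from the text. SAP 2.3.3 and the trigger in SAP 1.1 speak of treated patients without an enrollment condition. SAP 2.3.2 claims any safety analysis for the narrower set.

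**The case against.** The case for leaving the SAP alone has real content.

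- **A reader might infer that toxicity is dropped.** The documents do not support this. SAP 2.4.5, 2.2.1 and 2.2 keep these patients in the report. What they lose is a place in the rates, since a listing has no denominator.
- **A reader might infer that the exclusion reverses a GO/No GO decision.** This is not established. The exclusion in SAP 2.3 names only efficacy and all-treated populations. SAP 2.4.5 allows other populations where specified, and SAP 2.3.3 specifies one for the Bayesian design and the PSC analysis, worded by treatment. The model also only recommends stopping. Comparing 1/4 with 2/4, or 2/8 with 3/8, would overstate the effect because it holds n fixed.
- **Intended dose is not absolute.** It is a general presentation rule, and deaths depart from it. SAP Table 2 already classifies the actual dose at each infusion, so a wrongly dosed patient would be identifiable.
- **Such patients should be rare.** The IVRS/IWRS allocates the dose in Part 1. Protocol section 11 also leaves detailed definitions to the SAP, and the population diagrams are not available in the text to check how treated patients nest within enrolled ones.

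These points remove any claim of lost data or of a demonstrated change in the stopping rule. They do not remove the mismatch with protocol 11.3.1, the absence of a declaration in SAP 1.6, or the conflict between SAP 2.4 and 2.4.5.2. Detailing a definition is not the same as narrowing it without saying so.

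**Conclusion.** The concern holds in a limited form. The SAP's tabulated safety population is narrower than the protocol's and the change is undeclared. Its Part 1 dose grouping is by intention in general, unspecified in the safety section, and by receipt for deaths.

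The size depends on how many patients are dosed without randomization or given the other dose, which the documents do not state. If there are none, there is no effect. For one wrongly dosed patient with a PSC and 3/14 per arm as intended, the between-arm gap in PSC incidence is 11.3 points by dose received and zero by intended dose. The Bayesian recommendation would be sensitive to one omitted patient near the boundary and insensitive away from it, but only if the exclusion applies there, and the SAP leaves that open. The sample-size and response-rate calculations are untouched.

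**What to change.** - In SAP 2.3 and 2.3.2, define the safety population as all patients who received any amount of SAR566658, randomized or not, which restores protocol 11.3.1.
- In SAP 2.4 and 2.4.5, present Part 1 safety tables and PSC incidence by the dose received at first infusion. Using the first infusion means that a later dose reduction does not move a patient between arms. Deaths should follow the same rule.
- In SAP 2.3.3 and Appendix A, state that the PSC-evaluable population and the Bayesian model draw on this population and this dose.
- Enrolled patients and intended dose may be kept for efficacy. Because protocol 11.3.1 makes the any-dose set primary for efficacy too, declare that restriction in SAP 1.6.

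The cost is SAP wording and one derived variable for dose received at first infusion, which can use the bands already in SAP Table 2. It needs no extra patients and no protocol amendment.
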